### 7.10 Pharmacokinetic/Pharmacodynamic Blood Sample Collection and Processing

Plasma blood samples for pharmacokinetic/pharmacodynamic analysis of tivozanib levels will be collected via venipuncture using (2) 4 mL purple-top EDTA collection tubes per time point for PK and blood samples for sVEGF-2.

Pharmacokinetic/pharmacodynamic and sVEGF-2 sample collection will be obtained on:

- Cycle 1, Day 1 at pre-dose, 2 hours, and 4 hours post-dose.
- Cycle 1, Day 15 at pre-dose, 2 hours, and 4 hours post-dose.

Plasma will be separated from the total blood within 30 minutes following the extraction. The screw cap polypropylene cryogenic tube will be labeled with the subject identifier, subject's initials, subject's study number, clinical study number, protocol time point, dose, and protocol day. The label for each subject's sample will be supplied by RPCI. The samples will be placed in ice immediately and then frozen at -70°C or below until analyzed. After hours, samples will be processed in Lab Medicine.

**NETWORK SITES:** Follow directions above for sample collection and processing. The cryogenic tubes should be labeled with the Subject ID # (unique to Network patients), initials, the participant's study number, clinical study number, protocol time point, dose, and protocol day. The samples will immediately be frozen at -70°C or below (samples are to be stored until requested for batch mailing). Samples are to be batch shipped frozen, on dry ice.

Frozen samples will be shipped via Fed Express Overnight on dry ice with delivery on Mon-Fri. NO SATURDAY DELIVERY. Do not ship on a Friday or the day before a holiday.

Address shipments and any questions regarding specimen processing to:

Roswell Park Cancer Institute  
Bioanalytics, Metabolomics & Pharmacokinetics Core Facility  
[name]  
Refer to Study Number– I [229112](#)  
[name]  
[name]

[[contact]](mailto:[contact])

For additional information regarding the handling of pharmacokinetic samples please contact RPCI's Bioanalytics, Metabolomics & Pharmacokinetics Core Facility laboratory at [contact] (Tel) or [contact] (Fax).

**Note:** All investigator or analyzing research laboratories housing research samples need to maintain current **Temperature Logs** and study-specific **Sample Tracking and Shipping Logs**. The Principal Investigator/Laboratory Manager **must** ensure that the stated lab(s) have a process in place to document the receipt/processing/storage/shipping of study-related samples/specimens.

This is required for both observational and interventional clinical studies collecting clinical samples.

### 7.11 Immune Biomarker Blood Sample Collection and Processing

Blood samples for measuring immune correlatives by flow cytometry will be collected via venipuncture using (4) 10 mL green-top heparinized collection tubes. Tubes must be completely filled, and kept at room temperature until processing. Tube will be labeled with the subject identifier, subject's initials, subject's study number, clinical study number, protocol time point, and protocol day. The label for each subject's sample will be supplied by RPCI. Peripheral blood mononuclear cells (PBMC) will be isolated immediately by Ficoll-Paque™ PLUS density gradient centrifugation of blood samples. Refer to **Appendix F2.** Patient Pill Diary(Dose Reduced)

Study No.: \_\_\_\_\_ Patient's Name: \_\_\_\_\_

Drug Name: \_\_\_\_\_ Cycle: \_\_\_\_\_

Medical Record No.: \_\_\_\_\_

#### Study Medication Calendar for Tivozanib

You should swallow your medication, unchewed, with a large glass of water (about 8 oz.) in the morning every day with or without food. On days of a scheduled clinic visit, you should take your dose at the clinic after visit procedures are completed. If a dose is vomited or if you miss your dose for any reason, the dose should not be made up.

Please complete this calendar on a daily basis immediately after you take your pills. Fill in the date for each day and write the total number of pills you take each day.

Start Date: \_\_\_\_\_

Take 1 pill each time.

Cycle Day	Day 1**(dose1)	Day 2	Day3(dose2)	Day 4	Day5(dose3)	Day 6	Day7(dose4)
Time							
Date							
Number of pills taken							

Cycle Day	Day 8	Day 9(dose5)	Day 10	Day11(dose6)	Day 12	Day13(dose7)	Day 14
Time							
Date							
Number of pills taken							

Cycle Day	Day15(dose8)	Day 16	Day17(dose9)	Day 18	Day19(dose10)	Day 20	Day 21
Time							
Date							
Number of pills taken							

Cycle Day	Day 22	Day 23	Day 24	Day 25	Day 26	Day 27	Day 28
Date	No medication is to be taken during this time.						
Number of pills taken							

\*\*Do NOT take your pill on Day 1 until your blood is drawn and the study staff instructs you to take it.

Roswell Park Cancer Institute Study Number: I 229112

---

Please remember to bring this calendar and your pill bottle (including any unused pills) with you to your next clinic appointment.

**Coordinator's Use Only**

$$\% \text{ Compliance} = \left( \frac{\text{Number of Pills Dispensed} - \text{Number of Pills Returned}}{\text{Number of Pills Scheduled}} \right) \times 100$$

$$\text{---}\% \text{ Compliance} = \left( \frac{\text{---} - \text{---}}{\text{---}} \right) \times 100$$

Patient's Signature: \_\_\_\_\_

Date: \_\_\_\_\_

CRC Signature: \_\_\_\_\_

Date: \_\_\_\_\_

Investigator Signature: \_\_\_\_\_

Date: \_\_\_\_\_

Appendix G for the SOP for PBMC isolation.

Sample collection will be obtained on: Tube station 611

- Predose on Cycle 1, Day 1
- Cycle 3, Day 1
- When the patient progresses/comes off study drug or at 1 year whichever occurs first.

For patients enrolled at RPCI, four 10 mL green-top heparinized blood collection tubes will be sent to tube station 611 for processing on the same day. PBMCs from the tubes will be isolated by members of the [name] laboratory according to the SOP in Appendix F (Section 1). Cells will be stored in liquid nitrogen at RPCI as described in Appendix F Section 2 & 3. PMBCs will be analyzed by members of the [name] laboratory when all three samples from an individual patient are available in order to minimize assay variability.

For patients enrolled at Network Sites, four 10 ml green-top heparinized blood collection tubes will be processed on the same day at the Network Site. PBMCs will be isolated by trained, designated staff at the Network Site according to the SOP in Appendix F (Section 1). Cells will be stored in liquid nitrogen at the Network Site as described in Appendix F (Section 2 & 3). PMBCs will be shipped to RPCI via Federal Express overnight delivery on dry ice (Monday – Thursday only) when all three samples from an individual patient are available.

For Network sites, batched samples must be shipped overnight on dry ice Monday – Thursday only via Federal Express delivery. There is **NO SATURDAY DELIVERY. Do not ship on a Friday or the day before a holiday.**

[name]  
Roswell Park Cancer Institute  
[name]  
Center for Genetics and Pharmacology  
[name]  
[name]

For additional information regarding the handling of laboratory samples please contact RPCI's [name] Laboratory at [contact], [contact], [contact] or [[contact]](mailto:[contact]).

Isolated PBMCs will be stored in liquid nitrogen in 90% human AB serum plus 10% DMSO. All 3 samples from an individual patient will be analyzed simultaneously to minimize assay variability. Extensive testing has been performed to compare fresh and frozen thawed samples for reproducibility and to ensure that the process of freezing does not influence the viability of cells types being evaluated. FACS analysis on the various cell subsets will be performed as

described in detail in the study methodology section. Plasma samples will be stored at  $-80^{\circ}\text{C}$  for future measurement of inflammatory and immunosuppressive cytokines.

Clinical therapy, outcome and baseline demographic data will be recorded and stored in the RPCI clinical research database. These will be merged with immune data analyzed in blinded fashion and provided to the statistician for analysis.

**Note:** All investigator or analyzing research laboratories housing research samples need to maintain current **Temperature Logs** and study-specific **Sample Tracking and Shipping Logs**. The Principal Investigator/Laboratory Manager **must** ensure that the stated lab(s) have a process in place to document the receipt/processing/storage/shipping of study-related samples/specimens. This is required for both observational and interventional clinical studies collecting clinical samples.

## 8 EFFICACY EVALUATIONS

### 8.1 Objective Tumor Response

All protocol-defined imaging studies must be performed at the investigative site or sponsor-approved facility using protocol-defined parameters. The same method of assessment and the same technique should be used to characterize each identified and reported lesion at baseline and during follow-up. RECIST 1.1 will be used to assess objective tumor response.

### 8.2 Target Lesions

All measurable lesions up to a maximum of 2 lesions per organ and 5 lesions in total, representative of all involved organs, will be identified as target lesions and recorded and measured at baseline. Target lesions will be selected on the basis of their size. Lesions with the longest diameter (short axis for lymph nodes) and are  $\geq 10$  mm (CT and MRI),  $\geq 15$  mm lymph nodes,  $> 20$  mm CXR and are for accurate repetitive measurements (either by imaging techniques or clinically) will be chosen. A sum of the longest diameter (short axis for lymph nodes) of all target lesions will be calculated and reported as the baseline sum diameters. This will be used as reference to further characterize the objective tumor response of the measurable dimension of the disease.

- **Complete Response (CR):** Disappearance of all target lesions. Any lymph nodes must have a reduction in short axis to  $< 10$  mm. Changes in tumor measurements must be confirmed by repeat studies performed no less than 6 weeks after the criteria for response are first met.
- **Partial Response (PR):** At least a 30% decrease in the sum of diameters of target lesions, taking as reference the baseline sum diameters. Changes in tumor measurements must be confirmed by repeat studies performed no less than 6 weeks after the criteria for response are first met.
- **Progressive Disease (PD):** At least a 20% increase in the sum of diameters of target lesions, taking as references the smallest sum on study (this includes the baseline sum if that is the smallest on study). In addition to the relative increase of 20%, the sum must also demonstrate

an absolute increase of at least 5 mm. The appearance of one or more new lesions is also considered progression.

- **Stable Disease (SD):** Neither sufficient shrinkage to qualify for PR nor sufficient increase to qualify for PD, taking as reference the smallest sum diameter while on study. Subjects having a documented response with no confirmation of the response will be listed with stable disease.

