### 3.3.3 Treatment Cycle

A cycle will be defined as 28 days. At the full dose, this will be 21 days on treatment with 7 days off. However, in the case of a dose reduction patients will be treated starting on day 1 of the cycle, every other day for 10 doses. Treatment will continue until progression or toxicity. Response/ progression will be assessed Q 8 weeks or q 2 months by CT scan. (MRI when patients have contraindication to CT). Steady state PK will be assessed at Day 15, as this is the first study in patients with liver dysfunction.

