**7.4 Evaluations Performed at Day 1 of Each Cycle After Cycle 1 ( $\pm$  3 Days)**

- Physical examination, including vital signs (i.e., temperature, heart rate, respiratory rate, blood pressure, and body weight)
- Hematology (i.e., complete blood count (CBC) with differential, absolute neutrophil count (ANC), and platelets)
- Chemistry (comprehensive metabolic panel (i.e., AST, ALT, total bilirubin, alkaline phosphatase, creatinine, potassium, glucose, and calcium) and serum albumin.
- PT/INR
- ECOG Performance Status
- Tivozanib (Patients will take at home).
- Concomitant Medications
- Adverse Events
- Alpha Fetoprotein (AFP): Biomarker to detect hepatocellular cancer every 2 cycles, starts with cycle 3 (Only if elevated at baseline).
- A computed tomography scan (CT scan) every 2 cycles, not to exceed 10 weeks apart.
- Urine will be collected to look at protein and creatinine levels every 2 cycles starting with cycle 3
- If either (or both) HBsAg or Hep C Ab with verification are positive, blood will be collected for viral load, (Hep B (or C) virus PCR, Quant) every 2 cycles starting with cycle 3

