
1 Performed within 2 weeks prior to treatment start and prior to receiving any study-related procedures.
 
2 Height collected at baseline only.
 
3 Hematology (i.e., complete blood count (CBC) with differential, absolute neutrophil count (ANC), and platelets).
 
4 Chemistry (comprehensive metabolic panel (i.e.; AST, ALT, total bilirubin, alkaline phosphatase, creatinine, potassium, glucose, and calcium) and serum albumin).
 
5 Only test if AFP was elevated at baseline.
 
6 Refer to Section 7.10.
 
7 Pre-dosed cycle 1 day 1, cycle 3 day 1, when the patient progresses/comes off study drug or at 1 year whichever occurs first. Refer to Section 7.11.
 
8 Performed within 1 week prior to treatment start.
 
9 Only if last CT scan was more than 28 days prior to end of treatment.
 
10 Patients will be administered tivozanib in clinic following their pre-dose pharmacokinetic/pharmacodynamic sample.
 
11 Medications ongoing within 1 week prior to first dose of study drug.
 
12 CT every 2 cycles starting with cycle 3, with maximum of 10 weeks apart.
 
13 Collect viral load, pre-treatment, if either (or both) HBsAg or Hep C Ab with verification are positive & every 2 cycles starting with cycle 3.
 
14 Every 2 cycles starting with cycle 3.
 
15 Patients will be followed for overall survival, every 6 months by medical record review
 
16 CT scan within 4 weeks prior to treatment start.
 
17 Only if unknown
							

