### 8.4 Evaluation of Response

Time point response assessments will be performed every 8 weeks (timed to coincide with the end of a cycle) with a confirmatory assessment (required for non-randomized trials) within 6 weeks after a PR or CR is deemed. To determine time point response, refer to **Table 5** and below.

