### 8.5 Confirmation Measurement

Response will be confirmed within 6 weeks.

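### Sections 8.2 and 8.4/8.5 set opposite limits on when a response must be confirmed; routine CT meets only 8.2, so CR and PR counts depend on which section is applied

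*Combined protocol and SAP*

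**What the plan says.** Section 8.2 attaches the same sentence to both CR and PR: "Changes in tumor measurements must be confirmed by repeat studies performed no less than 6 weeks after the criteria for response are first met". Its stable disease entry adds a default: "Subjects having a documented response with no confirmation of the response will be listed with stable disease".

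Section 8.4 schedules response assessments every 8 weeks, "with a confirmatory assessment (required for non-randomized trials) within 6 weeks after a PR or CR is deemed". Section 8.5, whose only subject is confirmation, is one sentence: "Response will be confirmed within 6 weeks". Section 8.4 also makes best overall response subject to any confirmation requirement.

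On imaging, Table 4 footnote 12 reads "CT every 2 cycles starting with cycle 3, with maximum of 10 weeks apart", and Section 7.4 gives the same frequency and cap. Section 3.3.3 fixes the cycle: "A cycle will be defined as 28 days". Visits after Cycle 1 carry a window of ±3 days. The only other post-baseline CT in Table 4 is at end of treatment, done if the last CT was more than 28 days earlier (footnote 9; Section 7.7).

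**The concern.** One section gives 6 weeks as the earliest time for confirmation and two give it as the latest. Nothing in the protocol says which governs. An unconfirmed response is downgraded to stable disease, so the conflict reaches the data: the same images can yield a PR or an SD depending on the sentence applied. In a multicenter, unblinded, single-arm trial, sites could classify differently. The rule could also be chosen after the responses are known, which would weaken any response rate reported.

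**Working it through.** The plan states no figure on this point, so there is none to reproduce. The check compares day windows.

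**Inputs**
- Section 8.2: gap d from first response to confirming scan ≥ 6 × 7 = 42 days.
- Sections 8.4 and 8.5: d ≤ 42 days.
- Routine CT: every 2 cycles of 28 days (Sections 3.3.3 and 7.4), nominal gap 2 × 28 = 56 days.
- Visit window: ±3 days at each end, so 56 − 6 = 50 to 56 + 6 = 62 days.
- Cap: 10 × 7 = 70 days.
- End-of-treatment CT: day 29 or later after the previous CT.

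**Overlap of the two rules:** d ≥ 42 and d ≤ 42 leaves d = 42 only.

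| Scan after first response | Meets 8.2 | Meets 8.4/8.5 | Meets both |
|---|---|---|---|
| Next routine CT, days 50–62 | yes | no | no |
| Next routine CT delayed, up to day 70 | yes | no | no |
| End-of-treatment CT, days 29–41 | no | yes | no |
| End-of-treatment CT, day 42 | yes | yes | yes |
| End-of-treatment CT, day 43 or later | yes | no | no |
| Extra scan before day 42, not in Table 4 | no | yes | no |

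All 21 possible whole-day routine gaps from 50 to 70 (70 − 50 + 1 = 21) meet 8.2. None meets 8.4/8.5.

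**One patient followed through:** PR first seen at week 8 and still present at week 16, a gap of 56 days, with no scan between.
- Section 8.2 alone: confirmed PR.
- Sections 8.4/8.5 alone, routine scans only: unconfirmed, listed as SD.
- Both rules enforced on these scans: unconfirmed, listed as SD.

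**Where the label enters the analysis**
- Affected: best overall response (8.4); CR and PR counts; the logistic regression in 11.5, which defines clinical benefit as CR+PR; possibly the exploratory exposure analysis in 11.6, which does not define response.
- Not affected: the 24-week PFS endpoint (3.1); the two-stage rule, which counts PFS responders (11.2); the clinical benefit rate as CR+PR+SD (3.2, 11.6), since moving a patient from PR to SD leaves that sum unchanged.

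**Illustration only.** Assume 4 of 37 patients have a PR lasting over two routine scans. Under 8.2 the rate is 4/37 = 10.8% (exact 95% CI 3.0% to 25.4%). Under 8.4/8.5 with routine scans only it is 0/37 (upper limit 9.5%). The 4 is an assumption. Section 1.4 gives figures only for other tumors. In the solid-tumor Phase 1 study, disease control less stable disease is 46.3% − 43.9% = 2.4%, and 0.024 × 37 is about 1 patient. In renal cell carcinoma, 18% to 24.6% responded, and 0.18 × 37 to 0.246 × 37 is about 7 to 9 patients. The contrast could therefore be about 1 versus 0 or about 9 versus 0.

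**The case against.** The strongest reply is that Section 8.4 does not rely on routine scans. It calls for a separate confirmatory assessment, and Table 4 merely omits it. A site following 8.4 would order an extra scan, and the response would not be lost under 8.4/8.5. That stands. A reader might infer that every responder becomes stable disease, but the documents do not support this. The downgrade occurs only if the extra scan is not done, or if one scan must meet both rules. An early extra scan followed by the next routine CT would even satisfy each sentence, by different scans. The conflict remains all the same: the early scan confirms nothing under 8.2, and sites working from Table 4 would not know to order it.

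A reader might also infer that the schedule contains no scan inside 6 weeks. That is too absolute, because the end-of-treatment CT can fall on days 29 to 42. It is done only in a patient who is stopping treatment, so it is not a routine route to confirmation.

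The effect on endpoints is limited, and that stands in full. No objective response rate is listed as an endpoint. The clearest route into a planned analysis is the CR+PR label in Section 11.5, which itself disagrees with CR+PR+SD in Sections 3.2 and 11.6. Aligning those would close that route but would leave best overall response ambiguous.

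Finally, the protocol expects little shrinkage: Sections 1.1 and 2 describe benefit from targeted therapy in HCC without radiographic response. Few patients may be involved.

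**Conclusion.** The contradiction is real and in the current text. Sections 8.2 and 8.4/8.5 agree on one day only, and routine CT gaps of 50 to 70 days satisfy 8.2 alone. The result is ambiguity in the CR and PR counts and in whatever is built on them. It does not threaten the primary conclusion, and a reader should not infer that PFS, the stopping rule or the CR+PR+SD rate is compromised.

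The timing result assumes that scans follow the cycle visits and their ±3-day windows. The number of patients affected is unknown, and 10.8% versus 0% must not be read as an expected effect.

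**What to change.** Delete the 6-week maximum from Sections 8.4 and 8.5 and state one rule in 8.2, 8.4 and 8.5: *a CR or PR counts as confirmed when a later evaluable assessment, scheduled or end-of-treatment, at least 6 weeks after the response was first seen, still shows it.* Requiring specifically the next scheduled scan would be stricter than 8.2: a missed or non-evaluable scan, or a qualifying end-of-treatment CT, would then cost a patient confirmation. Apply the rule to all patients and fix it before response data are analysed.

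The cost is a short wording amendment with no added scans. There are two downsides. A responder with no later scan at 6 weeks or more stays unconfirmed. Any patient already classified on an earlier scan must be reclassified, which in an unblinded trial should be disclosed.

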### 8.3 Non-Target Lesions

All other small lesions (longest diameter < 10 mm or lymph nodes  $\geq$  10 mm to < 15 mm short axis) and non-measurable lesions (i.e., leptomeningeal disease, ascites, pleural or pericardial effusion, inflammatory breast disease, lymphangitic involvement of skin or lung, blastic bone lesions, or abdominal masses / abdominal organomegaly identified by physical exam that is not measurable by imaging) should be identified as non-target lesions and indicated as present in the source documents at baseline. The general location will also be documented on the images drawing a regularly-shaped Region of Interest. Measurements of the non-target lesions will not be performed, but the presence or absence of each should be noted throughout follow-up and evaluation.

- **Complete Response:** Disappearance of all non-target lesions and normalization of tumor marker level, if applicable. All lymph nodes must be non-pathological in size (< 10 mm short axis).
- **Non-Complete Response/Non-Progressive Disease:** Persistence of 1 or more non-target lesion(s) and/or maintenance of tumor marker level above the upper limits of normal.
- **Progressive Disease:** Appearance of 1 or more new lesions or the unequivocal progression of existing non-target lesions. Although a clear progression of non-target lesions is exceptional, in such circumstances, the opinion of the treating physician should prevail and the progression status should be confirmed at a later time.

### 8.4 Evaluation of Response

Time point response assessments will be performed every 8 weeks (timed to coincide with the end of a cycle) with a confirmatory assessment (required for non-randomized trials) within 6 weeks after a PR or CR is deemed. To determine time point response, refer to **Table 5** and below.

**Table 5. Time Point Response Criteria (+/- non-target disease)**

Target Lesions	Non-Target Lesions	New Lesions	Overall Response
CR	CR	No	CR
CR	Non-CR/Non-PD	No	PR
CR	Not evaluated	No	PR
PR	Non-PD or not all evaluated	No	PR
SD	Non-PD or not all evaluated	No	SD
Not all evaluated	Non-PD	No	NE
PD	Any	Yes or No	PD
Any	PD	Yes or No	PD
Any	Any	Yes	PD

